## Power analysis & sample size

The precise increase in steps/day necessary to reduce the risk of secondary health complications and disability post-stroke is not known, however, studies in other at risk populations have shown a reduction in cardiovascular events with an increase of 2,000 steps/day. Previous studies in chronic stroke, along with our data, suggest an improvement in ~1000 steps/day with fast walking training alone and our recent study suggests an improvement of ~1100 steps/day with a step activity monitoring program alone. Our data from the FAST+SAM intervention suggests an improvement of ~1700 steps/day in those with low steps/day at baseline and an improvement of ~250 steps/day for those in FAST with low baseline steps/day. Given this, we would consider an average improvement of  $\geq 1700$  steps/day in the FAST+SAM group worthy of further study in future clinical trials. Power calculations indicate that a total of 225 participants

are needed (75 in each of the 3 groups) in order to detect this differential increase based on baseline steps/day and intervention received with power greater than 0.90. These calculations assume equal group sizes, a moderate correlation among repeated measures of  $r=0.50$ , and a standard deviation for steps/day of 2,500.

### **Expected outcomes and aim specific analysis**

**Aim 1.** To compare the efficacy of the FAST+SAM, FAST and SAM interventions for improving real-world walking activity in chronic stroke survivors and to determine for whom the interventions are most effective. The primary measure for this Aim is number of steps per day (SPD). Data will be calculated at each time point (Baseline, post-treatment, 6 and 12 month follow-up) by finding the average number of SPD over one week.

*H1.1. All 3 interventions will improve real world walking activity immediately post-intervention.*

A GLMM will be used to evaluate changes in SPD from pre- to post-training. For this hypothesis the main effect of time will be compared, averaged across groups. If the main effect of time is significant, this research question can be answered using the marginal pairwise comparisons of SPD at baseline with post-training. If an interaction is significant, the simple main effect of time will be compared between interventions.

**Aim 2.** To compare the efficacy of the FAST+SAM, FAST and SAM interventions for improving walking speed, endurance and cardiorespiratory function in chronic stroke survivors and to determine for whom the interventions are most effective. The primary measure for this Aim is distance covered during the 6 minute walk test (6MWT). The secondary measures for this Aim are self-selected walking speed as measured during the 10 meter walk test (SSWS) and cardiorespiratory function as measured by peak oxygen consumption during graded exercise testing ( $VO_2$  peak). Data will be calculated at each time point (Baseline, post-treatment, 6 and 12 month follow-up).

The same exact analyses used in **Aim 1** for all the hypotheses will be used in Aim 2 but with the outcomes of 6MWT, SSWS and  $VO_2$  peak. Separate models will be completed for the 6 and 12 month time point.

**Updates to statistical analysis plan  
(excerpted from final IRB protocol  
(2023), ClinicalTrials.gov registry (2022))**

**General data management & analysis - all changes from initial plan were to incorporate use of REDCap electronic databases to increase data accuracy, accessibility, and security:**

Encrypted electronic files that connect subject identities to their subject code will be stored in a database on a password protected UD managed server for the UD and CCHS subjects. Similar processes are in place at UPenn and IU for their subjects. These files are not shared between sites. Paper copies of consent forms for each site will be stored on-site. Paper copies of the screening form for subjects that sign the Informed Consent are also stored at each site.

All coded subject data will be collected and managed using REDCap electronic data capture tools hosted by the University of Delaware's Delaware Rehabilitation Institute. REDCap (Research Electronic Data Capture) is a secure, web-based application designed to support data capture for research studies. All sites will have access to the coded data in the REDCap database.

Data from each evaluation session will be entered directly into the PROWALKS REDCap Clinical database. This database is designed with built in quality control checks (e.g., range checks, checking for missing data for required data points). In addition, each month the UD Research PT will examine frequency distributions of outcome variables to identify questionable data points.

Data from each training session will be entered directly into the PROWALKS REDCap Training database. This database is designed with built in quality control checks (e.g., range checks, checking for missing data for required data points). In addition, each quarter the UD Stroke Studies Coordinator will review a random sampling of data from 6 sessions at each site according to the Treatment Fidelity checklist webform.

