(FAST+SAM) is superior in improving real-world walking activity compared to fast walking training alone (FAST) or a step activity monitoring and feedback program alone (SAM) in those with chronic stroke. Using a randomized controlled experimental design, 225 chronic (> 6 months) stroke survivors, will complete approximately 12 weeks (goal of 36 sessions) of fast walking training (FAST), a step activity monitoring program (SAM) or a fast walking training + step activity monitoring program (FAST+SAM). The primary (steps per day), secondary (self-selected and fastest walking speed, walking endurance, oxygen consumption) and exploratory (vascular events, blood lipids, glucose, blood pressure) outcomes will be assessed by blinded evaluators prior to initiating treatment, after the last treatment and at a 6 and 12 month follow-up. Moderation of specific intervention outcomes by baseline characteristics will be evaluated to determine *for whom* the interventions are effective. Following completion of this study, we will not only understand the efficacy of the interventions and the individuals for which they are effective, we will have the necessary information to design a study investigating the secondary prevention benefits of improved physical activity post-stroke. This study is, therefore, an important step in the development of secondary prevention guidelines for persons with stroke.

[figure not shown]

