## **Testing Procedures**

***Baseline evaluation session.*** Subjects will undergo a brief battery of clinical assessments conducted by a trained member of the research team. Clinical assessments will include collection of medication and co-morbidity information, blood pressure, heart rate and body mass index, the 10 meter walk test, the 6 minute walk test, the Activities Specific Balance Confidence scale (ABC), the Patient Health Questionnaire nine-item depression scale (PHQ-9), and the Montreal Cognitive Assessment (MoCA) (see Appendices). In addition, subjects will be provided with a Stepwatch Activity Monitor and/or Fitbit activity monitor and instructed in its wear and use. Subjects will wear the monitor for 1 week. Following this baseline evaluation session and the 1 week step monitoring, the inclusion criteria of walking speed between 0.3 and 1.0 m/s and steps/day less than 8000, can be evaluated and continued eligibility confirmed. If subjects do not meet these criteria after evaluation, they will be withdrawn from the study.

If any subject scores  $\geq 5$  on the PHQ-9, they will be informed of their score and advised to discuss this with their primary physician. In addition, for any participant endorsing suicidal ideation on one or more test items on PHQ-9, (1) we will notify the physician and (2) we will give the participant the telephone number for Crisis Intervention Services of Northern Delaware ([[contact]]([contact]) or [[contact]]([contact])) which is staffed 24 hours/day, 7 days a week, to whom they can reach out if they feel desperate, hopeless and/or at risk for suicide. This is standard procedure for clients in the Physical Therapy Clinic.

Symptom limited graded exercise test. Prior to beginning the intervention, all subjects will undergo a symptom limited graded exercise test (GXT) on a motorized treadmill in the Nurse Managed Health Center (NMHC) under the supervision of a nurse practitioner and an exercise physiologist. During the GXT a 12 lead electrocardiogram and breath by breath analysis of oxygen consumption with a metabolic cart will be recorded. The results of the test will be reviewed by a cardiologist for abnormal responses that would prevent the subject from safe participation.

Subjects will have up to 5 ml of blood drawn by a trained practitioner in the NHMC for measurement of blood lipids and glucose at each of the testing time points (baseline, post-intervention and 6 and 12 month follow-up evaluation sessions).

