#### **Describe what exclusionary criteria, if any will be applied.**

The specific subject inclusion and exclusion criteria are:

**Inclusion Criteria:** 1) Age 21-85\*, 2) Chronic stroke (>6 months post stroke)\*, 3) Able to walk at self-selected speed without assistance from another person (assistive devices are allowed), 4) Self-selected walking speed <1.0 m/s\*, 5) Average steps/day <8,000, 6) Resting heart rate between 40-100 beats per minute\*, 5) Resting blood pressure between 90/60 to 170/90\*.

**Exclusion Criteria:** 1) Evidence of cerebellar stroke\*, 2) Other potentially disabling neurologic conditions in addition to stroke\*, 3) Lower limb Botulinum toxin injection <4 months earlier, 4) Current participation in physical therapy, 5) Inability to walk outside the home prior to the stroke, 5) Coronary artery bypass graft, stent placement or myocardial infarction within past 3 months\*, 6) Musculoskeletal pain that limits activity, 7) Inability to communicate with investigators, 8) score >1 on question 1b and >0 on question 1c on the NIH Stroke Scale, 9) Self-selected walking speed <0.3 m/s\*.

*\*For recruiting participants from the Stroke Research Registry, criteria with asterisks represent data found in the Registry and may be used in search queries to more efficiently find individuals to contact who would be qualified to participate in this study.*

The inclusion and exclusion criteria are discussed at the initial screening and again on the first

testing day when the informed consent document is reviewed. Determining whether all criteria on the Inclusion and Exclusion Criteria Checklist (see Appendices) are met is based on a combination of subjects' individual responses and information from other documentation. Two inclusion criteria (walking speed between 0.3 and 1.0 m/s and steps per day <8,000) cannot be evaluated until the baseline evaluation is completed. Therefore, subjects will be withdrawn from the study if these criteria are not met following this evaluation.

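### H1.1 infers that all three interventions work from an uncontrolled before-after rise in steps/day, measured from the same week that screens out people at 8,000 or more

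*Combined protocol and SAP*

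**What the plan says.** The SAP (Expected outcomes and aim specific analysis, Aim 1) gives one hypothesis on the primary outcome: "All 3 interventions will improve real world walking activity immediately post-intervention". On the test it says: "For this hypothesis the main effect of time will be compared, averaged across groups". If that effect is significant, "this research question can be answered using the marginal pairwise comparisons of SPD at baseline with post-training". Arms are looked at separately only under a condition: "If an interaction is significant, the simple main effect of time will be compared between interventions". The SAP's update section reports no change to the aim-specific analyses.

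All three randomised groups (FAST, SAM, FAST+SAM) receive an active programme.

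The baseline count is described in item 6 of the protocol, Testing Procedures: "Subjects will wear the monitor for 1 week. Following this baseline evaluation session and the 1 week step monitoring, the inclusion criteria" of walking speed and of fewer than 8,000 steps/day can be judged. Item 7 adds that "subjects will be withdrawn from the study if these criteria are not met following this evaluation". No second baseline week, separate from screening, is described.

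The SAP's power section assumes a repeated-measures correlation of 0.50 and "a standard deviation for steps/day of 2,500". The Research Abstract (item 5) says "Moderation of specific intervention outcomes by baseline characteristics will be evaluated". The SAP's general analysis section provides for interaction terms, centred continuous predictors and simple-slopes probing.

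**The concern.** H1.1 is a causal statement answered by a comparison with no concurrent control. A rise between two monitored weeks may come from treatment, but also from season, getting used to the monitor, taking part in a study, or regression to the mean. With no untreated arm, the time effect cannot separate these.

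Regression to the mean is built in here, and it acts in the favourable direction. A week of step counts is a noisy measure of usual activity. Removing everyone at or above 8,000 in that week removes some people who happened to have a high week and keeps those who happened to have a low one. The retained baselines are therefore too low on average, and the next count tends to rise with no treatment effect. Testing each arm separately does not help, because the shift is present in every arm.

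What is at stake is a report that all three programmes increase real-world walking, on the primary outcome at alpha 0.05, when the design cannot show it. A related misreading concerns low-baseline participants: within any single arm they will tend to gain most even if nothing works.

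**Working it through.** **The plan's own figure.** The power statement concerns the differential increase by baseline and intervention, not H1.1. Take 1,700 v 250 steps/day (difference 1,450), 75 per arm, two-sided 0.05.
- Change scores: SD = 2,500 × √(2 × (1 − 0.5)) = 2,500; SE = 2,500 × √(2/75) = 408; 1,450/408 = 3.55; power = Φ(3.55 − 1.96) = 0.944.
- Baseline-adjusted: SD = 2,500 × √(1 − 0.25) = 2,165; power = 0.984.

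The stated power above 0.90 is reproduced if that difference applies to all 75 per arm.

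**Inputs for H1.1.** From the documents: SD 2,500, r = 0.50, cut-off 8,000, N = 225, alpha 0.05 (taken as two-sided, so 2.5% in the favourable direction). Assumed: normal step counts, no treatment effect, a mean before screening of 3,000 to 6,500, and r = 0.80 as an alternative.

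**Formulas.** With c = (8,000 − mean)/SD and λ = φ(c)/Φ(c):
- expected rise = (1 − r) × SD × λ
- retained baseline variance V = SD² × (1 − cλ − λ²)
- SD of change = √[(1 − r)² V + SD² (1 − r²)]
- chance of a significant rise = 1 − Φ(1.96 − rise/SE), with SE = SD of change/√225

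**Worked case, mean 5,000, r = 0.50.** c = 1.2 and λ = 0.2194. Rise = 0.5 × 2,500 × 0.2194 = 274. √V = 2,074. SD of change = √(0.25 × 2,074² + 0.75 × 2,500²) = 2,401. SE = 2,401/15 = 160. Chance = 1 − Φ(1.96 − 1.71) = 40%.

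| Assumed mean | λ | Screened out | Rise, r=0.50 | False improvement | Rise, r=0.80 | False improvement |
|---|---|---|---|---|---|---|
| 3,000 | 0.0552 | 2.3% | 69 | 6% | 28 | 4% |
| 4,000 | 0.1174 | 5.5% | 147 | 15% | 59 | 8% |
| 5,000 | 0.2194 | 11.5% | 274 | 40% | 110 | 18% |
| 6,000 | 0.3676 | 21.2% | 459 | 83% | 184 | 43% |
| 6,500 | 0.4591 | 27.4% | 574 | 96% | 230 | 61% |

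In a single arm of 75 at r = 0.50, the false-improvement rate for means of 3,000, 4,000, 5,000 and 6,000 is 4%, 8%, 17% and 39%.

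**Check on the normal model.** A normal curve with SD 2,500 puts Φ(−1.6) = 5.5% of people below zero steps at a mean of 4,000. Simulation that discards those impossible values gives pooled false-improvement rates of 2%, 25% and 78% at means of 4,000, 5,000 and 6,000 (r = 0.50), against 15%, 40% and 83% by formula. At 4,000 the cuts at 0 and 8,000 are symmetric about the mean and the shift cancels. The low-mean rows are therefore the least certain and could be nil.

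**If SD 2,500 describes enrolled rather than unselected people.** At r = 0.50 the rise is 244 for an enrolled mean of 3,500 and 493 for 4,000. At 4,500 the formula gives 1,131, but it needs an unselected mean of 6,761 with SD 3,764. The normal model is not reliable there.

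**Low-baseline gain within one arm, no effect.** For the lower half, before any cap, the gain is (1 − r) × 2,500 × φ(0)/0.5. This is 997 at r = 0.50 and 249 at r = 0.875.

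**Between-arm tests.** In 3,000 simulated trials with no effect and means of 4,000 to 6,000, the group test rejected in 4.3% to 4.7% and the group-by-baseline test in 4.3% to 5.4%, against a nominal 5%.

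**The case against.** The strongest reply is that the trial is comparative. Its stated objective, the rest of Aim 1 and the power calculation all concern differences between arms, which randomisation protects. The SAP is also labelled an excerpt and refers to several hypotheses while showing only H1.1. This stands, and it limits the point to H1.1 and within-arm readings.

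The size is also open to challenge. The pre-screening mean is not given. The protocol describes stroke survivors as very inactive and requires walking slower than 1.0 m/s, which favours the lower rows of assumed means. The correlation of 0.50 is a planning value, not a test-retest figure from untreated people. The plan cites a gain of about 250 steps/day for low-baseline FAST participants, far below the 997 that r = 0.50 predicts with no effect at all. If low means the lower half (the documents do not define it) and FAST does no harm, r is nearer 0.875. The rise is then 0.125 × 2,500 × λ, or 17 to 143 steps/day over means of 3,000 to 6,500, with false improvement in about 4% to 42% of trials. This too stands: the inflation may be modest.

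Two stronger readings are tempting, and the documents support neither.
- A reader might infer that regression to the mean accounts for the roughly 1,000 to 1,100 steps/day cited for FAST and SAM alone. Those are not given as low-baseline gains, so the lower-half figure is not a like-for-like comparison. The whole-group rise peaks at 574 in the table.
- A reader might infer that the question of who benefits is invalid. The plan already addresses it through interaction terms, simple slopes and a power target for the differential increase. No passage proposes to answer it from within-arm gains.

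None of this rescues H1.1. That an uncontrolled time effect cannot show causation needs no assumed mean or correlation.

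**Conclusion.** The concern holds for H1.1. As written, the rule can declare that the interventions improve walking when none does, because every arm is treated and the screening week is the baseline. The direction of the screening bias is favourable; its size is uncertain. Under normality and the plan's SD it is about 70 to 570 steps/day at r = 0.50 and 30 to 230 at r = 0.80 for assumed means of 3,000 to 6,500. It is close to nothing if the mean is low or the correlation high. It can explain statistical significance but, in these scenarios, not the full expected gain. The randomised contrasts and the arm-by-baseline interaction are intact. The matter should be fixed, as an error of interpretation in one hypothesis rather than a flaw in the trial's main comparison.

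**What to change.** 1. Restate H1.1 as descriptive change in steps/day within each arm, with confidence intervals, and say that no efficacy claim rests on it. Aim 2 reuses the Aim 1 analyses, so the same wording should carry over.
2. Rest efficacy on the randomised contrasts: FAST+SAM v FAST, FAST+SAM v SAM, and FAST v SAM.
3. State that conclusions about who benefits come from the arm-by-baseline interaction and its between-arm simple slopes, never from within-arm gains in low-baseline participants.
4. State whether a baseline week separate from screening exists.
5. If a regression-to-the-mean figure is reported, give it as a sensitivity range over the correlation. Use the step counts of everyone screened, including those withdrawn at 8,000 or more, because the formula needs the pre-screening mean. Do not plug in the correlation observed in enrolled, treated participants. At a mean of 5,500, truncation alone lowers a true 0.80 to 0.8 × 1,984/√(0.64 × 1,984² + 0.36 × 2,500²) = 0.73, which raises 1 − r from 0.20 to 0.27, over a third.

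The cost is SAP and report wording plus one supporting calculation. It needs no new participants, and no new data if screening counts of withdrawn people were kept. The downside is a weaker headline for H1.1.

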**Expected outcomes and aim specific analysis**

There were no changes to expected outcomes and planned aim specific analysis between the start and end of the study.

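### H1.1 claims that each of the three arms improves, but it is answered by the change averaged over arms, with arm-level change examined only after a significant interaction

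*Combined protocol and SAP*

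**What the plan says.** The SAP section on expected outcomes and aim specific analysis states H1.1 under Aim 1 (steps per day, the primary outcome): "All 3 interventions will improve real world walking activity immediately post-intervention". The analysis is a general linear mixed model of change from pre- to post-training, and "For this hypothesis the main effect of time will be compared, averaged across groups". If that main effect is significant, "this research question can be answered using the marginal pairwise comparisons of SPD at baseline with post-training". Arm-level change enters by one route: "If an interaction is significant, the simple main effect of time will be compared between interventions".

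Aim 2 states that the analyses of Aim 1 "for all the hypotheses will be used in Aim 2 but with the outcomes of 6MWT, SSWS and" VO2 peak. The later SAP update reports: "There were no changes to expected outcomes and planned aim specific analysis between the start and end of the study".

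The SAP section on general data management and analysis sets alpha at 0.05 for primary and 0.01 for secondary analyses, and applies Bonferroni adjustment to post-hoc tests in the mixed models. Nothing printed requires a test of each arm's own change when the interaction is not significant.

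**The concern.** The hypothesis is a conjunction: FAST improves, and SAM improves, and FAST+SAM improves. The pooled time effect tests whether the mean of the three changes differs from zero, and two effective arms can produce that without the third. The interaction test is meant to catch this, but a non-significant interaction does not show that the arms changed equally. Under the written rule it is nevertheless the condition on which the average is applied to all three.

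At stake is a report that a walking programme raises daily steps when its own arm did not change. The same logic carries to 6-minute walk distance, walking speed and VO2 peak.

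**Working it through.** **Inputs from the SAP power section.** 75 per arm; SD of steps/day 2,500; correlation of repeated measures 0.50; gains of about 1,000 (FAST), 1,100 (SAM) and 1,700 (FAST+SAM, low baseline; also the target average), with about 250 for FAST at low baseline.

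**Assumptions.** Two-sided tests; equal SDs; complete data on 75 per arm; the gate is the 2-df arm-by-time F test at 0.05, because the text says only that an interaction must be significant.

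**The plan's own figure.** SD of change = 2,500 × √(2 × (1 − 0.50)) = 2,500. A between-arm difference in change has SE = 2,500 × √(2/75) = 408. For 1,700 − 250 = 1,450 steps/day, two-sided 0.05 power is 0.944, which agrees with the stated power above 0.90. That power is stated "in order to detect this differential increase based on baseline steps/day and intervention received with power greater than 0.90". It is not power for H1.1.

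**The H1.1 rule.**

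1. SE of one arm's change = 2,500/√75 = 289. SE of the pooled change = 2,500/√225 = 167.
2. Gate noncentrality λ = 75 × Σ(μᵢ − μ̄)²/2,500², on 2 and 222 df. At 1,100/0/1,100 (order FAST+SAM/FAST/SAM) the mean is 733, the squared deviations sum to 806,667, and λ = 75 × 806,667/6,250,000 = 9.68, so gate power is about 0.80. The pooled change is 733/167 = 4.4 SEs, so the time effect is almost always significant.
3. The false all-three rate is the share of trials with a significant positive time effect and a closed gate. It was obtained by simulation (200,000 to 400,000 trials per pattern), with gate power checked against the noncentral F.

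| True gains | Gate opens | Time significant, gate closed | All three arms pass their own 0.05 test |
|---|---|---|---|
| 1,700/0/1,100 | 0.971 | 0.029 | 0.024 |
| 1,700/1,000/0 | 0.969 | 0.031 | 0.023 |
| 1,400/0/1,100 | 0.905 | 0.095 | 0.024 |
| 1,100/0/1,100 | 0.795 | 0.204 | 0.024 |
| 1,000/1,000/0 | 0.711 | 0.283 | 0.022 |
| 1,700/1,000/1,100 (all gain) | 0.360 | 0.640 | 0.900 |
| 1,700/250/1,100 (all gain) | 0.898 | 0.10 | 0.13 |

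The third column of the first five rows is error, as is the fourth; in the last two rows both are correct conclusions.

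4. After an open gate, Bonferroni-adjusted simple effects can also support the claim. Adding that route moves the two 1,700 patterns with a null arm only to 0.032 and 0.034. It brings the written rule to 0.845 at 1,700/1,000/1,100 and to 0.13 at 1,700/250/1,100.
5. With two arms at 1,000 and one at 0, the null arm's own test is non-significant in 0.258 of the 0.282 false claims. The data would usually show the problem, but the rule does not look.

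**The case against.** The plan does contain an arm-level step, and it works well when the arms differ as planned. With FAST+SAM at 1,700 and one component at zero, the gate opens in about 97% of trials and the false rate is near 3%, little more than with arm-level tests. The SAP gives positive gains for every arm and nowhere puts FAST+SAM at 1,000 or 1,100. All of this stands. A reader might infer from the last two null-arm rows that the plan's own figures imply a false claim in a fifth or more of trials. They do not: those rows need two departures from the SAP at once, a null component and a combination 600 to 700 steps/day below target.

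H1.1 is also not the trial's main question, which is whether and for whom FAST+SAM is superior. With no untreated arm, a per-arm pre-post test would not show causation either. This limits the consequence, but H1.1 is still a stated hypothesis on the primary outcome with a test that does not match it.

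A further objection is that arm-level tests would miss real but small gains. At 1,700/250/1,100 they confirm all three in about 13% of trials, but so does the written rule. At 1,700/1,000/1,100 they give 0.90 against about 0.85.

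A reader might also infer that the plan has no contrasts of FAST+SAM with each single arm. The documents do not support this: the SAP is labelled as excerpted and refers to hypotheses beyond the one printed. The H1.1 analysis itself is printed, so the present point does not depend on missing text.

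**Conclusion.** The mismatch is real and follows from the printed wording: a claim about each arm is answered by an average, and a non-significant interaction is the condition for stopping there. This is not a rare branch; at the planning gains of 1,700/1,000/1,100 the gate stays closed in about 64% of trials.

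The size is conditional: about 3% false all-three claims if FAST+SAM reaches 1,700, about 10% at 1,400/0/1,100, and 20–28% if the combination adds nothing to the effective single arm, against about 2% with arm-level tests. The null arm and the reduced FAST+SAM gains are assumed, and the rates would change if other interactions also open the gate. The rule is therefore weakest when the combination disappoints.

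For Aim 2 only the textual point holds. A reader might carry the rates across, but the documents give no SDs or expected gains for those measures.

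This should be fixed. It does not bear on the superiority or moderation questions.

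**What to change.** From the same mixed model, estimate each arm's pre-post change with a confidence interval whatever the interaction result. Claim that all three interventions improve only if every arm's change is significant in the direction of improvement at the alpha for that measure. State that the SAP's Bonferroni rule for post-hoc tests does not apply here: because every test must pass, no adjustment is needed. Apply the same rule to the Aim 2 measures.

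The cost is SAP wording, with the same model and data. Power for the all-three claim is 0.90 at 1,700/1,000/1,100, or 0.78 if Bonferroni were imposed. A true gain as small as 250 steps/day in one arm will usually not be confirmed, as under the present rule, so the intervals should be reported beside the verdict. If the change is made after data have been seen, label it as such.
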